Potentially eligible participants will be assessed via phone to determine whether they meet initial eligibility requirements. If eligible and interested, participants will be invited to Session 1 (pre Covid-19) or Session 2 (post Covid-19). They will be asked to abstain from smoking and all nicotine products (e.g., e-cigarettes) for 3 hours prior to attending this session, and told that confirmation of smoking status will be taken via a breath carbon monoxide (CO) measurement. There is no validated CO cut-off to confirm 3 hours of abstinence, so this is a “bogus pipeline” procedure, which has been found to improve accuracy of reported smoking behavior (Adams et al., 2008; Aguinis et al., 1993).

¹ Due to Covid-19 disruptions, after 3/13/20 additional safety precautions including minimizing participant contact were implemented. Aim 2 was powered for Session 2 (extinction), and cue reactivity was sufficiently demonstrated with the 17 participants who completed session 1 before the Covid-19 disruption in participant involvement. Thus, pre-Covid-19, participants attended both Sessions 1 and 2. Post-Covid-19, participants attend only Session 2 (extinction) and procedures were modified to accommodate a single session.

C.3.4. Procedure Overview for Session 1 and Session 2

At the beginning of Session 1 for pre-Covid-19 participants or Session 2 for post-covid participants, study staff will answer any questions the participants may have and the informed consent process will be completed. Participants will provide a breath CO sample and asked when they smoked their last cigarette, to confirm that they had abstained for 3 hours. Eligible participants will then complete a series of self-report questionnaires described below. We anticipate the informed consent and questionnaire phase will take approximately 45 minutes. Next, Session 1 pre-Covid-19 participants will complete the cue-reactivity procedures (about 45-60 minutes). Thus, Session 1 should take under 2 hours. Following this session, participants will be scheduled for Session 2 (extinction) within 120 days. Participants will be given similar pre-session abstinence instructions and asked to bring a pack of their own cigarettes. Again, this session will begin with self-report and CO assessment, and the full session is anticipated to last approximately 1.25 hours for pre-Covid-19 participants and 1.5-2.5 hours for post-Covid-19 participants.

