C.3.6.b. *In vivo Cues.* Presentation of in vivo cues will generally follow procedures used in the existing cue-reactivity literature (e.g., Wray et al. 2011; LaRowe et al., 2007). To match the AR cues for complexity and overall content, we will use 6 smoking and 6 neutral cues with matching content (e.g., if we use a pink eraser as a neutral cue for AR, a similar eraser will be used as an in vivo cue). Cues will be placed under numbered, opaque covers, and participants will be instructed when to uncover and re-cover each one during the trials. To control for assessment modality across Stimulus Type (AR vs in vivo), participants will answer urge questions via a smartphone app, similar to the AR app. Participants will also be encouraged to interact with the in vivo cues in a similar manner to the AR cues (e.g., walk around the cues to view from different distances and angles).

C.3.7. Session 1: Cue-reactivity

Session 1 will utilize a within-subjects design, so all participants will receive all cue presentations (see Figure 2 above). Because it would be difficult for participants to switch repeatedly between AR and in vivo cues, Stimulus Type (AR vs in vivo) will be presented in counterbalanced blocks. Within each block, we will randomize the presentation of smoking vs neutral cues. Figure 3 is a visual depiction of the stimulus-presentation strategy. Each cue will be presented for 15 seconds. Participants will complete the urge question at baseline and will then complete the urge question and reality/co-existence questions (for AR only) immediately following each cue presentation. To reduce carryover effects, each stimulus presentation will be

separated by 1 minute, during which participants will engage in a neutral activity (e.g., solving easy word search puzzles). The general procedures are similar to those commonly found within the literature (e.g., Carpenter et al., 2009; LaRowe et al., 2007; Wray et al., 2011). In sum, participants will complete baseline urge questions, view a cue for 15 seconds, complete urge and/or reality/co-existence questions, complete the word search for 1 minute, view another cue, and so on, until all 24 cues have been presented. The cue-reactivity procedures should last under 1 hour.

C.3.8. Session 2: Extinction

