The 2x2 within-subject design for Session 1 will provide measures of urge to smoke and reality/co-existence (for AR only) for analysis. Smoking cue-reactivity will be computed for both the AR and the in vivo conditions by subtracting the average urge to smoke (1-10 scale) following smoking cues from the average urge to smoke following neutral cues; higher scores represent greater smoking cue-reactivity. Based on the existing literature (Carter & Tiffany, 1999), we expect in vivo smoking cue-reactivity equivalent to a Cohen's $d = 1.0$, a very large effect. In terms of urge to smoke, this approximates an average difference score of 2.0 units with a standard deviation of 2.0.

Support for the effectiveness of AR to generate smoking cue-reactivity will be evaluated in two ways. First, average AR smoking cue-reactivity will be tested against a minimal threshold of Cohen's $d = 0.5$ (i.e., expected 1 unit on the urge to smoke scale) using a single-sample t-test. Second, the equivalence of the AR and in vivo stimuli toward generating smoking cue-reactivity will be evaluated using two one-sided tests (TOST) for equivalence.

The 142 participants completing Session 1 will be randomly assigned to the extinction or control condition in Session 2. With an estimated attrition of 10%, 128 are expected to complete Session 2. One measure of extinction will be the difference in urge to smoke at Trial 27 from urge to smoke at Trial 2, such that more positive values represent greater extinction of AR smoking cue-reactivity. Extinction based on this measure will be evaluated using a between-groups t-test. In addition, growth curve modeling will be used to compare the trajectories of urge to smoke using each self-report during the presentation of stimuli with the hypothesis of a greater negative slope for the extinction condition. Finally, the secondary measure of latency to smoke following the extinction trials will also be evaluated using a between groups t-test.

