Sample size was driven by the power required for Session 2. Power was estimated using PASS 15 (2017). With 128 participants in Session 2 (64 per condition), alpha = .05, and a two-sided test, Power will $\geq .80$ to detect a Cohen's $d \geq .50$ (a medium effect size) using the t-test. *A medium effect size is consistent with most of the existing cue-exposure treatment literature on cravings to smoke despite variations in population, types of cues (e.g., visual, audio, in vivo), number of exposures, massed or spaced exposures and number of participants. Cohen's $ds = .20, .45, .52, .75, 1.15$ for studies with reported effect sizes or with effect sizes that could be easily calculated for smoking urges (Niaura et al., 1999; Corty and McFall, 1984; Lowe et al., 1980; Kamboj et al., 2012; Unrod et al., 2014). Although an effect size was not reported, Collins et al. (2011) found significant reductions in cravings following repeated cue exposure despite having a substantially smaller sample size ($N = 42$). Studies that did not find an exposure effect were severely underpowered with Ns ranging from 7 to 32 (Götestam & Melin, 1983; Raw & Russel, 1980; Lee et al 2004; [name] et al., 2012; Miranda et al. 2008; and LaRowe et al. 2007).* Growth curve modeling of urge to smoke will have greater power presuming reliable measurement. The 142 participants completing Session 1 will yield power $> .95$ to detect a small-medium ($d = .35$) AR smoking cue-reactivity effect that is greater than the minimal threshold (1 scale unit, $d = 0.5$). This N will also yield power $> .80$ using TOST with alpha = .05 to detect an average AR reactivity within 0.25 standard deviations of the average in vivo reactivity (expected 2 scale units, $d = 1.0$).

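### The Session 1 AR versus in vivo tests omit the block order that the design counterbalances, so any block-to-block change in the smoking-neutral urge gap stays in the error variance

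*Combined protocol and SAP*

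**What the plan says.** Section C.3.7 makes Session 1 fully within-subject: "Stimulus Type (AR vs in vivo) will be presented in counterbalanced blocks". Inside a block the two cue types are mixed: "Within each block, we will randomize the presentation of smoking vs neutral cues". Section C.3.6.b ties the contents of the two modalities together: "we will use 6 smoking and 6 neutral cues with matching content". The sequence runs "until all 24 cues have been presented", which is 12 contents in each of two modalities, with a one-minute neutral task between cues to limit carryover.

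Statistical Design and Power, Aim 2, defines reactivity within each modality by "subtracting the average urge to smoke (1-10 scale) following smoking cues from the average urge to smoke following neutral cues". Read literally, that reverses the sign, because higher scores are then said to mean more reactivity. I take it as smoking minus neutral. Two tests follow. AR reactivity is compared with a threshold of d = 0.5 (1 urge unit) by a single-sample t-test, and "the equivalence of the AR and in vivo stimuli toward generating smoking cue-reactivity will be evaluated using two one-sided tests (TOST) for equivalence". Neither test has an order, period or sequence term, and order is not among the listed moderators. Section C.3.5 describes assignment for Session 2 but not how Session 1 block order was allotted.

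Footnote 1 says Session 1 stopped at the Covid-19 disruption and that "cue reactivity was sufficiently demonstrated with the 17 participants who completed session 1 before the Covid-19 disruption". The power text for Session 1 still uses 142.

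**The concern.** If each modality forms one block, Session 1 is in effect a two-period crossover, and the second block repeats the first block's contents in the other modality. Section A.3 rests on the idea that repeated cue presentation without smoking weakens the cue response. On the plan's own premise, then, reactivity could be lower in the second block. Counterbalancing keeps such a change from favouring one modality, but an unadjusted paired analysis leaves it in the residual spread.

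Footnote 1 leaves 17 people as the only direct AR versus in vivo comparison, and section C.5 says similar reactivity would be strong support for the programme. With so few people, avoidable error variance is worth removing. Because 17 is odd, the two orders also cannot be equal in number.

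**Working it through.** **Inputs from the documents.** SD of a reactivity score 2.0 units, expected mean 2.0 (Statistical Design and Power, Aim 2). Equivalence margin 0.25 SD = 0.5 unit, alpha .05, planned n = 142 (power paragraph). Actual n = 17 (footnote 1).

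**Assumptions.** The correlation rho between AR and in vivo reactivity, the block change g and the order split are not given. I use rho = .5, .75 and .9; g = 0.5 and 1 unit; and a 9/8 split, the nearest to equal.

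**Reproducing the plan's figure.** SD of the paired difference = 2.0 × √(2(1 − rho)), which is 2.0 at rho = .5. Paired TOST power, normal form, true difference 0: 2Φ(0.5√142/2.0 − 1.645) − 1 = 0.818; the exact value is 0.813. This agrees with the stated power above .80, so rho = .5 fits the plan's figure.

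**Effect of omitting order.** Let the smoking-neutral gap change by g from block 1 to block 2. The paired difference (AR minus in vivo) then has mean δ − g in the n1 people who see AR first and δ + g in the n2 who see in vivo first.

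- Unadjusted mean: δ + g(n2 − n1)/n. At 9/8 the shift is g/17 in size: 0.03 at g = 0.5 and 0.06 at g = 1.
- Unadjusted expected variance: SD² + g² × 4·n1·n2/(n(n − 1)). At 9/8 the multiplier is 288/272 = 1.059.
- Adjusted estimate: average of the two order-group means, with SE = SD × √(1/n1 + 1/n2)/2 on 15 df.

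For SD 2.0 and g = 1, the unadjusted SD is √(4 + 1.059) = 2.249 and the 90% half-width is 1.746 × 2.249/√17 = 0.95. The adjusted half-width is 1.753 × 2.0 × √(1/9 + 1/8)/2 = 0.85.

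| rho | paired SD | g | unadjusted 90% half-width | adjusted | too wide by |
|---|---|---|---|---|---|
| .5 | 2.00 | 0.5 | 0.87 | 0.85 | 3% |
| .5 | 2.00 | 1 | 0.95 | 0.85 | 12% |
| .75 | 1.41 | 0.5 | 0.64 | 0.60 | 6% |
| .75 | 1.41 | 1 | 0.74 | 0.60 | 23% |
| .9 | 0.89 | 0.5 | 0.44 | 0.38 | 15% |
| .9 | 0.89 | 1 | 0.58 | 0.38 | 52% |

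**AR threshold test.** Here order moves a person's score by ±g/2 about the average over block positions, so the variance term is a quarter as large. At SD 2.0 and g = 1 the SD is √(4 + 0.265) = 2.065, about 3% wider.

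**Effect on the TOST at n = 17, 9/8, g = 1** (simulated power, unadjusted against adjusted): 0.0001 against 0.0006 at rho .5; 0.002 against 0.026 at rho .75; 0.03 against 0.42 at rho .9.

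**Uneven splits.** The shift is 3g/17 = 0.18g at 10/7 and 7g/17 = 0.41g at 12/5. Under simple coin-flip allotment, which the plan does not describe, a split of 12/5 or worse has probability 0.14.

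**The case against.** Several objections have force.

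- **Not every block change matters.** Smoking and neutral cues are mixed within each block and reactivity is their difference, so a general drift in urge cancels in expectation. A reader might infer that any first-to-second-block change distorts the comparison. The documents do not support that; only a change in the gap does.
- **Large changes are hard to expect.** A first block gives six smoking cues of 15 seconds, 90 seconds in all. Session 2 gives 24 smoking cues of one minute and is powered for d = .50. A 1-unit change would remove half of the expected 2.0-unit reactivity. At 0.5 unit and rho .5 the cost is 3%.
- **The error is conservative at a near-equal split.** Sampling variation of the mean does not include g, but its estimated SE does. A reader might suspect a false claim of equivalence, yet wider intervals make one less likely.
- **Adjustment seldom changes the conclusion.** At rho .5 the TOST has almost no power with 17 people either way. At a paired SD of 1.1 and g = 0.5, the half-width falls from 0.51 to 0.47, on either side of the 0.5 margin, but power rises only from about .09 to .16.
- **The layout is partly inferred.** Figure 3 is not shown and may give the order scheme.
- **The data have been judged.** Footnote 1 already draws a conclusion from them, so an order term now would be post hoc.

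These points limit the size and status of the concern. They do not supply the missing order term or the achieved split.

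**Conclusion.** The point holds as one of precision and reporting. Both planned Session 1 tests leave out a factor that the design deliberately balances. The loss is small at the correlation that reproduces the plan's own power and for a modest block change. It becomes material only with a high AR to in vivo correlation, a large change in the gap, or both, and neither quantity is in the documents.

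Two stronger conclusions are tempting and unsupported. One is that the AR versus in vivo estimate is biased. At 9/8 the shift is negligible, and no passage reports a worse split; at 12/5 with g = 1 it would be 0.41 unit against a 0.5-unit margin, which is why the split should be stated. The other is that an order term would rescue the equivalence test. The main limit there is 17 people against power stated for 142, which is a separate matter.

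**What to change.** In Statistical Design and Power, Aim 2, Session 1:

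1. Regress each person's AR minus in vivo reactivity difference on block order, effect-coded as AR first or in vivo first. Take the estimate, 90% CI and TOST from the intercept.
2. Fit AR reactivity the same way for the comparison with 1 unit.
3. Report the number of people in each order, how order was allotted, and the order effect.
4. Show the unadjusted results alongside, and label the adjusted ones as added after Session 1 data were seen.

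The cost is a short addition to the SAP, no new data and one degree of freedom. With no block effect, the 90% half-width at SD 2.0 goes from 0.847 to 0.852 at 9/8 (0.6% wider) and is about 2% wider at 10/7. At 12/5 it would be 0.933, about 10% wider, in exchange for removing the shift. The order term does not remove carryover that differs between modalities.

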Aside from those already described, the following measures will be administered at Session 1 for pre-Covid-19 participants and at Session 2 for post-Covid-19 participants. *Demographics and Smoking History* will collect data on variables including gender, age, race, marital status, income, education, and smoking history (e.g., number of quit attempts, years smoked). *Fagerström Test for Nicotine Dependence* (FTND; Heatherton et al., 1991) is a widely used measure of nicotine dependence. *Wisconsin Smoking of Withdrawal Scale* (WSWS; Welsch et al., 1999) is a well-validated measure used to assess various facets of nicotine withdrawal. *Positive and Negative Affect Schedule* (PANAS; Watson et al., 1988) is a self-report measure that assesses an individual's positive and negative affect at a given point in time. We will also administer the *Brief Wisconsin Inventory of Smoking Dependence Motives* (WISDM-38), a multidimensional assessment of motivational factors associated with smoking behavior (Smith et al., 2010). We are particularly interested in the Cue Exposure/Associative Processes scale, which assesses the degree to which a participant's smoking is driven by cue-reactivity. Therefore, we will include the full subscale from the original WISDM-68 (Piper et al., 2014), due to its superior psychometrics (Smith et al., 2010). Aside from their descriptive value, these additional measures will allow for testing moderators of cue-reactivity and extinction.

Summary of Changes Pre and Post-Covid-19		
	Pre-Covid-19	Post-Covid-19
N	17	128
Session(s)	Session 1 and Session 2	Session 2 only
Consent and Survey administration (demographics, smoking history, etc.)	Session 1	Session 2
Length of Session(s)	1.25 hours	1.5-2.5 hours
Compensation	\$40 Session 1; \$50 Session 2	\$60

C.3.11. Data Management and Statistical Considerations

See Statistical Design and Power attachment, as per new instructions for Clinical Trial applications.

C.4. Aim 3: Initial Translation into Intervention-Ready App

C.4.1. Project Overview

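### Session 2 conditions differ between the pre- and post-Covid cohorts, but the Aim 2 analyses have no cohort term and do not say whether the 17 pre-Covid participants are included

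*Combined protocol and SAP*

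**What the plan says.** **The change in procedure.** Footnote 1 in Aim 2 records that 17 people attended both sessions before Covid, and that afterwards "participants attend only Session 2 (extinction) and procedures were modified to accommodate a single session". In Session 1 (C.3.7) participants gave an urge rating after each cue "until all 24 cues have been presented". The cues were six each of AR smoking, AR neutral, in vivo smoking and in vivo neutral. After Session 1, "participants will be scheduled for Session 2 (extinction) within 120 days" (C.3.4). On the questionnaires, C.3.10 states that "the following measures will be administered at Session 1 for pre-Covid-19 participants and at Session 2 for post-Covid-19 participants". C.3.4 puts the consent and questionnaire phase at about 45 minutes. C.3.8 gives Session 2 as 1.25 hours pre-Covid and 1.5 to 2.5 hours post-Covid.

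**The analysis.** C.3.5 stratifies randomisation by sex and cigarettes per day, not by cohort. Under Statistical Design and Power, Aim 2, one extinction measure is the urge change between Trial 2 and Trial 27. "Extinction based on this measure will be evaluated using a between-groups t-test". Growth curves and a t-test on latency follow, and moderators are tested one at a time through an interaction term. None of these models has a term for cohort or period.

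**The numbers.** The statistical section starts from 142 people who complete Session 1 and continues: "With an estimated attrition of 10%, 128 are expected to complete Session 2". It does not mention the Covid change. C.3.1 gives 128 as the Session 2 sample size. C.3.2 and the table in C.3.10 give 128 as the post-Covid cohort alone, next to 17 pre-Covid.

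**The concern.** The two cohorts reach Trial 1 by different routes. The pre-Covid group has seen the AR smoking cues before; the post-Covid group has not. The post-Covid group completes the full questionnaire set on the day, so its time since the last cigarette at Trial 1 may be longer. The protocol treats both factors as relevant: C.3.7 spaces cues to limit carryover, and C.5 says that reactivity is often higher under acute deprivation.

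If the 17 are analysed with the others and no cohort term is used, any cohort difference in the change score goes into the error variance. Latency has no within-person baseline that could absorb such a difference. If pre-exposed participants extinguish less, the powered contrast is diluted and nothing in the plan would show it.

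A separate issue concerns the WSWS (withdrawal) and PANAS (affect), which measure states. If either is used as a moderator of extinction, post-Covid values come from the same day, while pre-Covid values may be up to 120 days old.

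Aim 2 decides whether Aim 3 goes ahead as planned (C.5). How to handle 12% to 13% of the sample should therefore be settled before the data are seen.

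**Working it through.** **Inputs from the documents.** "With 128 participants in Session 2 (64 per condition), alpha = .05, and a two-sided test", with power of at least .80 claimed at d = .50; 17 pre-Covid and 128 post-Covid participants; blocks of 8 in four strata.

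**Assumptions (the documents give no figures).** A cohort shift *s* of 0.25 to 1.0 SD in the change score; strata equally likely; d = .50 expressed in within-cohort SD.

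**1. The plan's own figure.** Noncentrality = d / √(1/n₁ + 1/n₂) = 0.5 / √(2/64) = 2.83 on 126 df. The noncentral t gives power .801, so the stated figure reproduces. At N = 145 (73 and 72 per arm) power is .849.

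**2. Cost of leaving out the cohort term.** With cohort share p, the variance is inflated by 1 + p(1 − p)s², and the effective d is 0.5 divided by the square root of that.
- N = 128: p = 17/128 = .133, p(1 − p) = .115.
- N = 145: p = 17/145 = .117, p(1 − p) = .103.

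| s (SD) | Power, N = 128, no term | Power, N = 145, no term |
|---|---|---|
| 0.25 | .799 | .846 |
| 0.5 | .790 | .840 |
| 1.0 | .757 | .812 |

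With the term (1 df), power is .801 and .848.

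**3. Chance imbalance of the 17 between arms.** Simulating blocks of 8 in four equal strata gives a mean arm difference of about 0, an SD of 2.7 and a 95th percentile of 5 participants (11 v 6). With s = 1.0 at N = 128, that moves the estimate by 5/64 = 0.08 SD, against a standard error of √(2/64) = 0.18. Simulated type I error of the t-test without a cohort term, with s = 1.0 and 64 per arm, is .045.

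**4. Dilution if pre-exposed participants respond less.** Pooled d = 0.5 × (1 − p) with no effect in the 17, and 0.5 × (1 − p/2) with half the effect.
- No effect: d = .434, power .68 at N = 128; d = .441, power .75 at N = 145.
- Half effect: d = .467, power .75 at N = 128; d = .471, power .80 at N = 145.

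These are illustrations. No passage indicates that the effect is weaker in the 17.

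**5. Post-Covid-only analysis.** If 128 includes the 17, then 128 − 17 = 111 remain (56 and 55 per arm) and power is .742. If the total is 145, 128 remain and power is .801.

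**The case against.** The strongest reply is that the primary contrast is largely protected. Both cohorts are randomised to the same two conditions and the measure is a within-person change. Earlier exposure to AR smoking cues was only 6 × 15 seconds = 90 seconds, against 24 one-minute extinction trials. At N = 145 the test keeps power above .80 even with a 1 SD cohort shift. This stands, and it limits the point to precision and robustness.

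Several stronger readings are tempting, and the documents do not support them:

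- *The plan pools the cohorts.* No passage says so. Because 128 is both the Session 2 size and the post-Covid size, the 17 may lie outside the set, inside the 128, or on top of it. Inclusion is plausible: footnote 1 has them attending Session 2, no passage excludes them, and the statistical section would use Session 1 measures as Session 2 moderators. But that section describes the two-session design for everyone, so it does not settle the matter.
- *Post-Covid participants wait 45 minutes longer after the abstinence check.* In C.3.4 consent comes before the check, and the 45 minutes covers both consent and questionnaires. The added delay is shorter. Pre-Covid Session 2 also opens with some self-report.
- *WSWS and PANAS are planned moderators in the statistical section.* They are not named there. C.3.10 says only that the additional measures make moderator tests possible, and such tests are exploratory. The instruments in the pre-Covid Session 2 self-report are not listed, so a same-day repeat cannot be ruled out.
- *Trial 2 is invalid as a pre-test for the 17.* C.3.8 uses the term for a trial before the extinction series and does not claim first exposure.

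It is also fair to object that a main-effect cohort term cannot repair or reveal dilution of the effect. That is why the sensitivity analysis is needed as well.

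**Conclusion.** The point holds as a gap in the analysis plan of minor to moderate priority. Conditions in and before Session 2 changed by cohort. The statistical section was not brought into line: the Session 2 analysis set is undefined and no model, stratum or sensitivity analysis reflects the change.

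A reader might infer a biased primary result, but that does not follow. The arm contrast is unbiased in expectation and type I error is not inflated. For an assumed 0.5 SD cohort shift, omitting the term costs about one point of power (.801 to .790 at N = 128; .849 to .840 at N = 145). At 1.0 SD and N = 128 it costs about four points. The larger losses under dilution depend on an assumed weaker effect in the 17. The case for acting is that the remedy is nearly free, not that the expected harm is large. If the sponsor intends to leave the 17 out, the cohort term becomes unnecessary, but that decision also has to be written down.

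**What to change.** In Statistical Design and Power, Aim 2:

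1. State whether the Session 2 analysis set is 128 or 145, and if 128, whether the 17 are inside it. Reconcile this with the 142 and 128 now given.
2. If the 17 are included, add a cohort indicator (two-session v single-session) to the change-score and latency models, and cohort and cohort by time to the growth model.
3. In that case, also name a sensitivity analysis that reports the extinction effect in post-Covid participants only.
4. If WSWS or PANAS is used as an exploratory moderator of extinction, use only values taken on the day of Session 2. The FTND and WISDM, which are closer to traits, can be used from either session.

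Cost: SAP wording, one covariate already on file (1 df in the change-score and latency models; power stays at .801 for N = 128), and one extra run. The state-moderator models may lose up to 17 participants. If the 17 are inside the 128, the post-Covid-only analysis has power of about .74, so it should remain a sensitivity analysis. Any comparison of the effect between cohorts will be imprecise with 17 people in one of them.
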